8. STATISTICAL METHODS AND ANALYSIS

8.1 General Statistical Conventions

All statistical procedures will be completed using SAS 9.4® or higher.

Unless otherwise stated, all statistical testing will be two-sided and will be performed using a significance (alpha) level of 0.05, and two-sided 95% confidence intervals (CI) will be provided when relevant.

Continuous variables will be summarized using descriptive statistics, including number of subjects (n), mean, median, standard deviation (SD), minimum and maximum. For efficacy variables with subscales, the total score and subscales will be summarized.

For categorical variables, summaries will include counts of subjects and percentages. Percentages will be rounded to one decimal place.

Unless otherwise stated all summaries will be presented by treatment group.

All subject data, including those derived, will be presented in individual subject data listings. Unless otherwise stated, unscheduled visit results will be included in date/time chronological order, within subject listings only. All listings will be sorted by treatment group, subject ID, date/time and visit/study day. Subject's sex and age will be stated on each listing. Unless otherwise stated, data listings will be based on All Subjects Randomized Set.

8.2 Subject disposition

Subject disposition information will be tabulated for all screened subjects, including rows for all screened subjects, randomized subjects (total and by whether or not treated), and screen failures (total and by reason).

A separate table will describe disposition for all randomized subjects, by treatment group and overall. The table will provide rows for the number of randomized subjects and the number of treated subjects (i.e., the mITT population), as well as the numbers and percentages (based on the mITT population) of subjects who completed the double-blind period, who entered the open-label period, who completed the entire study, and who withdrew early (by period). The primary reason for early withdrawal will also be tabulated.

The number and percentage (using the mITT population as the denominator) of subjects in each analysis set will also be tabulated.

By-subject disposition listings will be provided separately for screened subjects who were not in the ITT population and for subjects in the mITT population.

Treatment Misallocations:

If a subject was randomized but took incorrect treatment throughout the double-blind period, they will be reported under the randomized treatment group for all efficacy analysis, but will be reported under the treatment they actually received for all safety analysis. However, if a subject took the incorrect treatment for only part of the time during the double-blind period, they will be reported under the randomized treatment group for all efficacy and safety analysis. The subjects who took incorrect treatment intermittently will be identified, and Ad Hoc analyses may be performed.

Protocol deviations

All key protocol deviations (categorized) will be summarized by treatment group and overall, using the mITT population. Subjects excluded from the mITT population to yield the Per-Protocol population will be listed, with reason for exclusion, treatment group, age, sex and race. A by-subject listing will include the inclusion/exclusion criteria violated at Screening and at Baseline Visits as well as other protocol deviations identified, based on data recorded on the eCRF and/or protocol deviation logs from ICON Medical (on Randomized subjects).

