9 INVESTIGATIONAL PLAN

9.1 Overall Study Design and Plan

9.1.1 Description

This is a randomized, double-blinded, placebo-controlled, 2-arm study, with an open-label extension period following double-blind treatment, to investigate the anti-pruritic efficacy and safety of NAL ER tablets. Eligible subjects will be randomized to NAL ER (2-week titration followed by 162 mg BID for 12 weeks) or matching placebo (14 weeks duration), with the primary endpoint evaluation at Week 14. If permanent discontinuation of investigational product occurs anytime between Day 1 and the Week 14 visit, the subject must be asked to complete the Off-Treatment visit, the Last Visit, the End of Study telephone call, and to return to the clinic for the study planned Week 14 visit (unless consent is withdrawn). During the open-label extension, subjects who received NAL ER will continue on NAL ER for a total of 38 additional weeks (total treatment duration 52 weeks including titration) and subjects who received placebo will

crossover to NAL ER for a total of 38 weeks (including titration). Upon discontinuation of investigational product, all subjects will complete the 2-week off-treatment and safety follow-up period, regardless of when and why the subject discontinued study treatment, unless they withdraw consent. In addition, a final follow-up itch and safety assessment will be made via the End of Study telephone call 4 weeks after the last dose of investigational product. The total planned study duration from randomization through to the last telephone contact is 56 weeks.

Approximately 360 subjects with diagnosed PN will be randomized (1:1) to one of the following treatment arms:

Arm 1: Blinded active titration over 2 weeks (to achieve a final NAL ER dose of 162 mg) followed by 162 mg BID for 12 weeks with continuation into the extension titration period (blinded), and the open-label fixed-dose period, followed by a 2-week off-treatment safety follow-up period and a final telephone contact, for itch and safety assessment, 4 weeks after investigational product discontinuation.

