10.1.1 Administration of Study Treatments

Double-blind Treatment

Following randomization, the subject will be dispensed a 2-week blister card for the double-blind titration period. Dosing will consist of 3 tablets for the AM dose and 3 tablets for the PM dose. Arm 1 will consist of a combination of 27 mg/54 mg/placebo tablets, and Arm 2 will consist of placebo tablets only. Note: Although both AM and PM doses are present on Day 1, only the PM dose will be taken (both Arms).

At the Week 2 end of titration visit, subjects in Arm 1 will be given one 70 count bottle of NAL ER 162 mg tablets and subject in Arm 2 will be given one 70 count bottle of placebo tablets. Additional bottles will be dispensed at subsequent study visits. At each visit at which investigational product is to be dispensed, enough investigational product should be supplied to ensure that a sufficient number of tablets are available for dosing until the next visit, allowing for visit windows and/or the possibility of a late visit.

Subject dosing information for the double-blind treatment will be available in the Pharmacy Manual provided to the site. Additionally, all subjects are to be provided with the “Instructions for Taking TR11 Study Medication” which outlines dosing instructions for this treatment period.

Open-label Treatment

Subjects will be dispensed a 2-week blister card for the extension titration period. Dosing will consist of 3 tablets for the AM dose (starting on Day 2) and 3 tablets for the PM dose. (Note: There will not be any tablets to take on Day 1 AM for both Arms 1 and 2). For subjects previously assigned to Arm 2 of the double-blind treatment, the titration card will consist of combinations of either 27 mg/54 mg/placebo tablets to crossover to NAL ER. To maintain the blind, subjects previously assigned to Arm 1 will be given a card containing 3 active 54 mg NAL ER tablets for the AM dose and 3 active 54 mg NAL ER tablets for the PM dose.

At the Week 16 end of titration visit, all subjects will be given 1 x 70-count bottle for the start of the open-label fixed-dose period containing 162 mg NAL ER tablets. Additional bottles will be dispensed at subsequent study visits and subjects should again be dispensed enough investigational product to ensure that a sufficient number of tablets are available for dosing until the next visit, allowing for visit windows and/or the possibility of a late visit.

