6.2. Safety population (Safety)

The safety population will consist of all randomized subjects who have received at least a single dose of the investigational product. The safety population will be used in all safety analyses. In the event of a discrepancy between the randomized treatment and the actual treatment received, subjects will be analyzed according to the treatment they actually received.

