8.7 Safety analyses

Safety summaries will be conducted on the safety population (treated subjects) and will be performed for all safety variables specified below:

- Adverse events;
- Laboratory tests;
- Vital signs;
- Central Electrocardiograms (ECG);
- Brief neurological assessments;
- Physical Examinations;
- SOWS.

All safety data will be summarized by treatment group.

The safety summaries of changes from baseline to a specific time point in safety variables (e.g., laboratory parameters, vital signs, and ECG) will only include subjects from the safety population who have data available for both the baseline and the time point under consideration unless otherwise specified. No statistical tests will be performed.

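### SAP 8.2 keeps partly misallocated subjects in their randomised arm for safety, so events a placebo subject has on NAL ER are tabulated as placebo, out of line with the as-received rule in SAP 6.2 and protocol 13.3.3

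*SAP*

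**What the plan says.** SAP 6.2 sets a general safety rule for any mismatch between assigned and actual treatment: "subjects will be analyzed according to the treatment they actually received". Protocol 13.3.3 has the same rule. Neither mentions duration or mixed exposure.

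SAP 8.2, under Treatment Misallocations, splits the cases. A subject on the wrong treatment for the whole double-blind period stays in the randomised arm for efficacy, "but will be reported under the treatment they actually received for all safety analysis". Where the error covered any shorter stretch, the rule is different: "they will be reported under the randomized treatment group for all efficacy and safety analysis". No minimum or maximum duration or dose is set. The only follow-up is this: "The subjects who took incorrect treatment intermittently will be identified, and Ad Hoc analyses may be performed".

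SAP 8.7 adds: "All safety data will be summarized by treatment group". SAP section 9 lists five changes from the protocol, and this is not among them.

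**The concern.** A reader of SAP 6.2 or protocol 13.3.3 expects safety columns to reflect the drug taken. SAP 8.2 applies that only when the wrong drug was taken for the entire period. For anything shorter it falls back on assignment. A programmer working from 6.2 and one working from 8.2 could place the same subject in different columns.

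The case that matters is a placebo-randomised subject who took NAL ER for part of the period. Events that begin while that subject is on NAL ER go into the placebo column, which makes the two arms look more alike. Such subjects may be informative. Protocol 9.3 says gastrointestinal and central nervous system effects come early and can limit treatment, and that titration is used to reduce them. Protocol 10.1.1 says the fixed-dose bottles for the active arm hold 162 mg tablets. An SAE or a discontinuation for an adverse event in that setting would count as placebo in the two parameters that protocol 13.4.7 names as key.

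Protocol 13.4.7 plans no formal safety testing and leaves inference to clinical review. The by-arm tables are therefore what reviewers will read, and column placement matters for that reason.

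**Working it through.** The plan states no figure on this point, so there is none to reproduce. The check compares the rules and then scales the effect.

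**1. The rules, case by case**

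| Double-blind exposure | SAP 6.2 and protocol 13.3.3 | SAP 8.2, safety |
|---|---|---|
| Wrong treatment throughout | Treatment received | Treatment received |
| Randomised to placebo, NAL ER for part | Received both; column not defined | Placebo |
| Randomised to NAL ER, placebo for part | Received both; column not defined | NAL ER |

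The documents agree in the first row. In the other two the general rule gives no single answer, and SAP 8.2 settles it by assignment.

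**2. How partial exposure can arise**

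A titration card is dispensed at baseline and bottles at Weeks 2, 6 and 10. Protocol 10.1.1 says of the bottles: "Additional bottles will be dispensed at subsequent study visits". One wrong dispensing therefore gives partial exposure. On the planned visit days:

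- Titration card, Days 1 to 14: 14 / 98 = 14.3% of the period.
- One bottle interval (Days 15 to 42, 43 to 70 or 71 to 98): 28 / 98 = 28.6%.
- All three bottle intervals: 84 / 98 = 85.7%.

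A placebo-randomised subject with a correct card but NAL ER bottles for all 84 fixed-dose days is still misallocated for only part of the period, and is reported as placebo.

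**3. Size of the effect on incidence**

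Protocol 9.1.1 gives the sample size: "Approximately 360 subjects with diagnosed PN will be randomized (1:1) to one of the following treatment arms". That is 360 / 2 = 180 per arm. The number of affected subjects is not given, so 1 to 5 is assumed here for scale only.

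- One placebo-randomised subject with an on-NAL ER event, who would not otherwise be counted in that row: 1 / 180 = 0.56 percentage points.
- Five such subjects: 5 / 180 = 2.78 percentage points.
- At the 120 per arm still stated in SAP section 5: 1 / 120 = 0.83 and 5 / 120 = 4.17 percentage points.

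**4. Size of the effect on exposure**

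SAP 8.7.1 also plans exposure-adjusted rates. If all 180 placebo subjects complete 98 days, one subject with 84 days on NAL ER contributes 84 / (180 × 98) = 84 / 17,640 = 0.48% of placebo exposure. The denominator barely moves, so the distortion comes from the events.

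**The case against.** The best counter-argument is that SAP 8.2 contradicts nothing. Treatment received has one meaning only when one treatment was received. A partly misallocated subject received both, the general rule is silent, and SAP 8.2 fills the gap. The protocol expects the SAP to add detail. This stands in part. A reader might infer a flat contradiction, but the documents show an incomplete general rule and a specific rule that resolves it against the as-received principle, with no cross-reference and no entry in section 9.

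Four further points are fair:

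- **Frequency.** A reader might infer that dispensing errors are nearly always partial, or put a percentage on them. Repeated dispensing makes partial errors possible, but the documents give no frequency for either kind.
- **Direction.** NAL ER-randomised subjects who took placebo for part of the period stay under NAL ER. That dilutes the NAL ER column, and a rule based on any NAL ER exposure would not change it.
- **Choice of remedy.** Moving a subject wholly to NAL ER after any dose would carry earlier placebo-period events with it. Assignment by onset avoids that but needs split exposure.
- **Existing safeguards.** SAP 8.1 requires individual listings, SAP 8.2 a by-subject deviation listing, and SAP 8.7.1 listings of deaths, SAEs and events leading to interruption or discontinuation. A careful reader could trace affected events.

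The safeguards soften the problem without removing it. The by-arm tables would still show on-drug events as placebo, and the only dedicated analysis is optional and undefined.

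**Conclusion.** The point holds as a small inconsistency that is cheap to correct. SAP 8.2 is out of line with the as-received rule in SAP 6.2 and protocol 13.3.3, SAP section 9 does not declare it, and it has no duration limit. For placebo-randomised subjects exposed to NAL ER, it moves on-drug events into the placebo column and shrinks the safety contrast.

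The size depends on a count that the documents do not give and that may be zero. Each affected subject with an event is worth about 0.56 percentage points at 180 per arm. A reader might infer that the safety conclusions are materially biased. The documents do not support that: no misallocation is reported, safety is descriptive, and efficacy is unaffected.

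**What to change.** - In SAP 8.2, remove the as-randomised exception for safety. Keep randomised assignment for efficacy.
- State one mixed-exposure rule in both SAP 6.2 and 8.2. In double-blind safety tables, a placebo-randomised subject's events with onset on or after the first NAL ER dose are reported under NAL ER, and earlier events stay under placebo. Split exposure time at the same point for the exposure-adjusted rates, and say how the subject enters the denominators of the simple percentages. NAL ER-randomised subjects stay under NAL ER.
- Replace the optional ad hoc analysis with a defined listing of every partly misallocated subject, in either direction, showing the dates of wrong treatment and all events with onset dates.
- Add the rule to SAP section 9.

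The cost is a few sentences and some programming to split exposure for the few subjects affected. No new data are needed. Two imperfections remain. Events after a subject returns to placebo would still count under NAL ER, and the dilution from NAL ER-randomised subjects given placebo is shown in the listing but not removed. If the SAP is already closed, its introduction gives the route: describe and justify the deviation in the clinical study report.

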8.3 Demographics and baseline characteristics

8.3.1 Demographics

Age, height, weight, BMI and other continuous demographic variables at baseline will be summarized descriptively using the mITT population. Sex, race, ethnicity and other categorical variables will be summarized using frequency counts and percentage for the mITT Population. By-subject listings will also be provided.

8.3.2 Baseline and disease characteristics (Prurigo Nodularis History)

The following categorical disease baseline characteristics will be summarized using frequency counts and percentages for the mITT population:

- When did the subject's Prurigo Nodularis start?
- If less than 3 months, did it start greater than 6 weeks ago?
- The quality of the itch
- What increases the itching?
- Scratching Behavior 1
- Scratching Behavior 2

- How does the subject perform the scratching?
- Previous treatments for Prurigo Nodularis

Data in Part 2 of the Prurigo Nodularis History represent Past Medical History (PMH) that may represent a risk factor for subsequent evolution of PN. Analyses of key efficacy endpoints will be performed for subgroups of sufficient size (See [Section 8.6.2](#)). These subgroups will combine subjects with relevant past medical histories based on the general understanding of the mechanism that may drive the association with itch. The following broad subgroups are anticipated, although the final grouping will be established based on the actual PMH data available prior to unblinding. Of note, the immune system may contribute to the itch component across these various categories and diseases, and if the understanding of PN itch evolves during the timeframe of the TR11 trial, these categories may shift.

- Subjects with a past history of *dermatologic diseases* associated with itch (atopic dermatitis, nummular or discoid eczema, venous stasis skin disorder, Epidermolysis Bullosa Acquisita, or other skin disease depending on type);
- Subjects with a past history of *metabolic diseases* associated with itch, or with other primary diseases thought for which itch induction is thought to act through a metabolic pathway, such as hepatic impairment (Diabetes, Diabetic or Non-Diabetic Kidney Disease, Chronic Anemia, Hypo- or Hyperthyroidism, Hepatitis B or C presumably mediated via hepatic dysfunction);
- Subjects with a non-dermatologic history of *atopic disease* (gluten enteropathy/Celiac disease, food allergy, environmental allergy, malabsorption/nutritional deficiencies);
- Subjects with a past history of neurological disease (peripheral neuropathy of hands/feet; other peripheral neuropathy; radiculopathy/sciatica; degenerative disc disease; degenerative vertebral bony disease; notalgia paresthetica; brachioradial neuropathy; trigeminal neuropathy; history of herpes simplex [severe] or herpes zoster infection);
- Other: subjects with a past history of various miscellaneous diseases expected to be of lower frequency (gastric ulcer disease, HIV infection, Haematologic malignancy, solid organ malignancy).

These conditions will be summarized using frequency counts and percentages using the mITT population, with the following categories for each condition: Yes, resolved; Yes, not resolved; No. Depending on

the completeness of the dates of onset and resolution, durations may be summarized with descriptive statistics.

By-subject listings will also be provided.

8.3.3 Neurological history

Neurological history will be summarized using frequency counts and percentages for the mITT population.

By-subject listings will also be provided.

8.3.4 Medical history

A summary of medical history will be presented by system organ class (SOC) and preferred term (PT) using Medical Dictionary for Regulatory Affairs® (MedDRA) Version 21.1 or higher. By-subject listings will also be provided.

8.3.5 Prior and concomitant medications

Medications used in this study will be coded using the latest available version of the World Health Organization Drug Dictionary Enhanced (WHODDE).

Prior medications: those medications taken (i.e., dosing documented) during the last 14 days prior to the first dose of study drug.

Concomitant medications (double-blind period): those medications taken (i.e., dosing documented) at any time from the first dose of study medication date through the end of the subject's double-blind participation.

Concomitant medications (open-label period): those medications taken (i.e., dosing documented) at any time from the start of the open label titration period (i.e., day of first dose of open label titration study drug supplies) through the date of the last dose of study medication.

Prior medications and concomitant medications will be summarized descriptively using frequency tables by Anatomical Therapeutic Chemical' (ATC) class and generic name by treatment group for the mITT population and presented separately for the following groups:

- Prior medications;
- Concomitant medications taken during the double-blind treatment period;
- Concomitant medications taken during the open-label period;
- Medications taken during the first 14 days after the date of the last dose of study medication.

Details for imputing missing or partial start and/or stop dates of medication are described in

8.4 Extent of exposure

8.4.1 Treatment duration

The duration of double-blind period study drug (in days) will be calculated as: last dose date in the double-blind period – first dose date in the double-blind period + 1 day, regardless of study drug interruption.

The duration of the open-label period study drug (in days) will be calculated as: last dose date in the open-label period – first dose date in the extension titration period + 1 day, regardless of study drug interruption.

Duration of overall study drug (in days) will be calculated as: last dose date – first dose date + 1 day, regardless of study drug interruption.

Study drug exposure will be summarised by treatment group for the safety population using descriptive statistics. By-subject listings will also be provided.

8.4.2 Treatment compliance

Compliance in the double-blind period (%) = Number of double-blind period tablets subject actually took/ Number of double-blind period tablets subject was expected to take*100. In the double-blind titration period, a subject is expected to take 3 tablets in the AM and 3 tablets in PM for two weeks, with the exception of Day 1, on which they take only the PM dose. In the double-blind fixed-dose period, a subject is expected to take 1 tablet each in the AM and PM. The number of double-blind period tablets a subject was expected to take is the sum of {6 x [last dose date of double-blind titration – first dose date of double-blind titration +1] – 3} and {2 x [last dose date of double-blind fixed-dose – first dose date of double-blind fixed-dose +1]}. The number of double-blind period tablets a subject actually took will come from the pill counts from the eCRF, i.e., the number of tablets dispensed - the number of tablets returned from the blister cards and bottles for the double-blind period.

Compliance in the open-label period (%) = Number of tablets subject actually took during open-label period/ Number of tablets subject was expected to take during open-label period*100. The compliance is calculated similarly to the double-blind period. The number of tablets a subject was expected to take is the sum of {6 x [last dose date of extension titration – first dose date of extension titration +1] – 3} and {2 x [last dose date of open-label fixed-dose period – first dose date of open-label fixed-dose period +1]}.

Number of tablets a subject actually took during open-label period is calculated by the number of tablets dispensed - the number of tablets returned from the blister cards and bottles for the open-label period. Study drug compliance will be summarized by treatment group, with the number of subjects (n), mean, standard deviation, standard error, median, minimum, and maximum. They will also be summarized in categories “< 50% compliant” and “≥ 50% compliant” using frequency tables. Also, the categories of “< 60% compliant” and “≥60% compliant” will be provided by count and percentage. By-subject listings will also be provided.

Study drug compliance summaries will be based on the Safety Population.

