9.6 Premature Discontinuation of Investigational Product Treatment

Subjects who complete investigational product treatment through the full study treatment course are considered to have completed treatment with the investigational product (even if some doses have been missed). Subjects who discontinue investigational product, prior to 52 weeks of treatment will be considered to have prematurely discontinued and will be asked to complete the following visits (unless consent is withdrawn):

- If the decision to discontinue treatment is made during an onsite study visit (scheduled or unscheduled), perform the procedures and assessments outlined in the Off-Treatment visit, regardless of where they are in the study visit schedule.
- If the decision to discontinue treatment is made while the subject is not at a study visit, schedulea visit as soon as logically possible, but no later than 2 weeks later, to perform the procedures and assessments described in the Off-Treatment visit. Upon notification that the subject has permanently stopped dosing, the site should immediately update the subject’s status on the Trialogics web portal, in order to launch the SOWS, and instruct the subject to begin entering their SOWS data daily via the e-diary for the next 14 days.
- Schedule the subject to return to the clinic 2 weeks after completion of the Off-Treatment visit and perform the procedures and assessments outlined in the Last Visit, regardless of where they are in the study visit schedule.

- Schedule the End of Study telephone call with the subject 4 weeks after completion of the Off- Treatment visit and perform the procedures and assessments outlined in the schedule of events for this visit, regardless of where they are in the study visit schedule.
- If discontinuation of investigational product occurs any time between Day 1 and the Week 14 visit, the subject will be asked to complete the Off-Treatment visit, the Last Visit, and the End of Study visit telephone call, and to return to the clinic for the study schedule planned Week 14 visit.

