6.3. Per-Protocol population (PP)

The per-protocol (PP) population will include all subjects in the mITT population without any major protocol deviations that could have influenced the validity of the data for the primary efficacy variable.

The deviations can include, but are not limited to: e.g. inclusion criteria 1-6 and exclusion criteria 1-3, 16, 17, and 19-25 must have been satisfied.

- Key inclusion/exclusion criteria not satisfied.
- Use of prohibited concomitant medications.
- Inadequate investigational product compliance (<50% compliant), which will be determined before breaking the blind.

The subjects to be excluded from the PP population will be identified in a blinded fashion and documented in a memo prior to the database lock and unblinding.

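### Double-blind compliance is counted in tablets, so titration doses carry triple weight and a subject can clear the 50% per-protocol cut-off with about a quarter of the fixed doses

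*SAP*

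**What the plan says.** SAP 8.4.2 defines double-blind compliance as tablets taken over tablets expected, times 100. In titration "a subject is expected to take 3 tablets in the AM and 3 tablets in PM for two weeks"; the morning tablets of the first day are left out of the count. Afterwards the load drops: "In the double-blind fixed-dose period, a subject is expected to take 1 tablet each in the AM and PM".

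Both segments go into one denominator: "The number of double-blind period tablets a subject was expected to take is the sum of {6 x [last dose date of double-blind titration" minus the first titration date plus 1, less 3 tablets, added to "2 x [last dose date of double-blind fixed-dose" minus the first fixed-dose date plus 1. The numerator is tablets dispensed minus tablets returned, pooled over blister cards and bottles. SAP 7.2.4 takes the last date as the last dose actually administered, not the planned end of the period.

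SAP 6.3 then lists among the per-protocol exclusions: "Inadequate investigational product compliance (<50% compliant), which will be determined before breaking the blind". It does not refer to SAP 8.4.2, name a period, set a minimum exposure or mention stopping drug early. Protocol 13.3.2 gives no threshold and leaves it to be set before unblinding. Both lists are expressly non-exhaustive, and both documents call for a blinded memo naming the excluded subjects before database lock.

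Protocol 9.6 asks subjects who stop drug before Week 14 "to return to the clinic for the study schedule planned Week 14 visit".

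**The concern.** A compliance criterion for the primary endpoint should reflect how much of the target regimen was taken. The SAP ratio departs from that in two separate ways, which concern different subjects.

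- **Weighting.** Three tablets per titration dose against one per fixed dose means that two weeks of titration can offset many missed doses in the 12 weeks that follow.
- **Denominator.** Because the expected count closes at the subject's own last dose, time off drug before Week 14 never lowers the percentage.

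At stake is the per-protocol analysis of the primary endpoint. If subjects with little fixed-dose intake remain in that set, its result is pulled toward the mITT result and says less about the effect in subjects without major deviations.

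**Working it through.** The documents give a formula and a cut-off but no compliance result, so there is no stated figure to reproduce.

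**Inputs.** Titration of 14 days, 6 tablets a day, with 3 fewer on Day 1 (SAP 8.4.2). Fixed dose of 12 weeks, Days 15 to 98, or 84 days at 2 tablets a day (SAP III.A, 8.4.2). Exclusion below 50% (SAP 6.3).

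**Weight of titration**
- Tablets: 6 × 14 − 3 = 81 titration; 2 × 84 = 168 fixed dose; total 249. Titration share 81/249 = 32.5%.
- Doses: 2 × 14 − 1 = 27 titration; 168 fixed; total 195. Titration share 27/195 = 13.8%.

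**Fewest fixed doses that pass 50%, full card taken, last dose on Day 98**
- 0.5 × 249 = 124.5, so 125 tablets are needed.
- 125 − 81 = 44 fixed doses; 44/168 = 26.2%.
- In doses, the same subject took (27 + 44)/195 = 36.4%, which would fail.
- The result moves little with the last dose date: 42/164 = 25.6% for Day 96 and 46/172 = 26.7% for Day 100.
- The 60% reporting category in SAP 8.4.2 needs 150 tablets (0.6 × 249 = 149.4), so 69 fixed doses; 69/168 = 41.1%.
- One tablet a day throughout the fixed-dose period scores (81 + 84)/249 = 66.3%.

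**Full intake, then early stop.** At Day 14 the fixed-dose term is taken as zero.

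| Last dose | Taken / expected | SAP compliance | Share of 168 planned fixed doses |
|---|---|---|---|
| Day 14 | 81/81 | 100% | 0% |
| Day 21 | 95/95 | 100% | 14/168 = 8.3% |
| Day 28 | 109/109 | 100% | 28/168 = 16.7% |
| Day 42 | 137/137 | 100% | 56/168 = 33.3% |
| Day 56 | 165/165 | 100% | 84/168 = 50.0% |

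**Effect of the proposed measures**
- Fixed doses taken over fixed doses expected to last dose: the 44-dose subject scores 26.2% and fails. The once-daily subject scores 84/168 = 50% and stays, because exclusion is below 50%. Early stoppers with full intake still score 100%.
- Planned denominator of 168: stoppers at Day 42 or earlier in the table fail. The Day 56 stopper scores exactly 50% and stays.

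**The case against.** Several points on the other side stand and set the limits of this one.

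- **Blinded review can act.** The list is open, and by-subject compliance and exposure listings are planned (SAP 8.4.1, 8.4.2). A reader might infer that the SAP requires poor takers and early stoppers to stay in the set. It does not; it only lacks a rule that removes them.
- **SAP 8.4.2 is not the only definition.** Protocol 10.4 works by time interval and divides by tablets due or prescribed, recorded at each product return, and SAP 7.2.6 states the ratio in general form. That 8.4.2 governs the 50% cut-off is the natural reading, not a stated one.
- **The analysis is broader than adherence.** The protocol synopsis presents it as a check on protocol deviations, with concomitant medication as the example. Calling it a failed adherence test would overreach.
- **Early stoppers may supply little Week 14 data.** The Last Visit falls two weeks after the Off-Treatment visit, and the e-diary is collected there (Protocol 9.1.3.6, 9.6). A subject who stopped in Week 3 would normally have at most a web-portal score at the returning Week 14 visit, not a week of daily values. SAP 8.6 leaves missing Week 14 scores missing. A reader might picture a complete Week 14 average from such a subject; the visit schedule makes that unlikely. SAP 7.3.1 sets no minimum number of Week 14 values, though, so a contribution is not ruled out.
- **The 26% is a corner.** It needs every titration tablet taken and a last dose near Day 98. Sites review compliance at visits, and six consecutive missed doses in the fixed-dose period trigger contact with the Medical Monitor (Protocol 10.1.3, 10.4).
- **On-treatment compliance with duration reported separately is a coherent choice.** A planned-period denominator selects on an outcome of treatment. In TR03, 12 of 18 subjects on 162 mg completed against 20 of 22 on placebo. Response was 33.3% versus 18.2% in all treated subjects and 50.0% versus 20.0% in completers (Protocol 13.1). Such a rule could therefore favour the drug.

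None of this repairs the tablet weighting, which follows directly from the formula.

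**Conclusion.** The point holds as a defect in how the per-protocol compliance criterion is measured. Titration counts for 32.5% of the ratio against 13.8% of doses. In the limiting case the 50% cut-off admits a subject with 44 of 168 fixed doses (26.2%), and full intake up to an early stop always scores 100%.

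This assumes the nominal 14- and 84-day schedule and that SAP 8.4.2 supplies the figure used in SAP 6.3. The 26.2% also assumes a fully taken card; less complete titration raises the number of fixed doses needed. The documents give no basis for estimating how many subjects are affected.

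A reader might infer that the trial's main result is at risk. It is not: the primary analysis uses the mITT set, which no compliance rule touches. The likely direction of any effect is dilution of a supportive analysis. The weighting has a clean correction; the treatment of early stoppers is a trade-off and belongs in a sensitivity analysis.

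**What to change.** 1. In SAP 6.3, define the compliance criterion as fixed-dose AM and PM doses taken divided by fixed doses expected, from bottle counts only. Keep the 50% cut-off and cite the definition there. State how to classify a subject who took no fixed dose, since that ratio is 0/0.
2. Report titration compliance and the present pooled tablet ratio descriptively.
3. Add a labelled sensitivity version of the per-protocol analysis with the planned Day 15 to Week 14 denominator of 168 doses. State beside it that it may remove more active-arm than placebo subjects, and that it still keeps a subject who stops at Day 56.

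The cost is SAP wording, one derived variable and one extra run. Cards hold titration tablets and bottles hold fixed-dose tablets (Protocol 10.1.1), so existing counts separate the segments and no new data are needed. The per-protocol set may shrink somewhat. The rule should be fixed before unblinding; if that point has passed, present both versions as labelled sensitivity analyses.
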